1. SUMMARY

Residual congestion in hospitalized heart failure (HF) patients at discharge is one of the main causes of early readmission. The ReDS (Remote Dielectric Sensing) system is a non-invasive, easy-to-use, and rapid technique that accurately measures the proportion of fluid in lung tissue using RADAR technology. A pilot clinical trial (3 centers, 100 patients) led by the Principal Investigator (PI) demonstrated that guiding decongestion using the ReDS system during hospitalization was associated with a significant reduction in the 30-day readmission rate compared to standard clinical practice, without associated safety events.

Our current objective is to confirm the efficacy and safety of a ReDS-guided decongestion strategy in hospitalized congestive HF patients. To achieve this, an independent, randomized, single-blind clinical trial has been designed, enrolling up to 1,014 congestive HF patients in 25 Spanish hospitals. Patients will be randomized to a decongestion strategy, hospital discharge, and early follow-up in HF units based on ReDS system values versus a strategy based on current clinical practice. All patients will be evaluated daily during hospitalization and in two post-discharge visits (at approximately 10 and 30 days) in HF units using the ReDS system. However, information will only be available to clinicians in the intervention group.

The primary efficacy endpoint will be all-cause mortality, HF readmission, or HF-related decompensations at 30 days. The primary safety endpoint will be the rate of symptomatic hypotension, electrolyte imbalances, or worsening renal function at 30 days.

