4. OBJECTIVES

1. Primary:

1.1. To evaluate whether a ReDS-guided decongestion strategy during hospitalization for HF and early outpatient follow-up is superior to standard clinical practice in reducing the combined event rate of all-cause mortality, HF readmission, or HF visits requiring diuretic adjustment at one month.

2. Secondary:

- 2.1. To analyze the efficacy of a ReDS-guided decongestion strategy in specific clinically relevant subgroups (obesity, chronic renal insufficiency, diuretic resistance) and epidemiological subgroups (age and sex).
- 2.2. To correlate ReDS system measurements with plasma natriuretic peptide and CA125 levels at admission, discharge, and outpatient follow-ups.
- 2.3. To determine the safety of a ReDS-guided decongestion strategy compared to standard clinical practice at one-month post-discharge by evaluating renal function deterioration, symptomatic hypotension, and electrolyte imbalances.
- 2.4. To calculate the cost-effectiveness of a ReDS-guided decongestion strategy considering hospital stay duration and reduction of the combined efficacy endpoint.

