5. METHODOLOGY

5.1. Study design (annex 1)

A randomized, single-blind, controlled, multicenter clinical trial (list of investigators and participating centers in annex 2) promoted by the researcher, which evaluates the efficacy and safety of a decongestion strategy guided by the ReDS system compared to standard clinical practice in patients admitted for decompensated heart failure.

5.2. Study population

Those adult patients meeting all the following criteria will be included:

- 1. Hospitalized due to HF as the main reason, including the presence of symptoms and signs of congestion, regardless of the left ventricular ejection fraction (LVEF).
- 2. NT-proBNP greater than 1000 pg/L or BNP greater than 300 pg/L upon admission.

Patients meeting any of the following conditions will be excluded:

- 1. Height less than 150 cm or greater than 190 cm or body mass index (BMI) less than 22 or greater than 39, conditions where the use of ReDS is not approved.
- 2. Patients requiring inotropes or vasopressors upon admission, with mechanical support, or heart transplant recipients.
- 3. Any malformation or variant affecting the right lung anatomy (e.g., a pacemaker).
- 4. Patients with any heart disease requiring a planned surgical intervention during the clinical trial (coronary disease, valve disease, or other).
- 5. Chronic kidney disease on hemodialysis.
- 6. Life expectancy less than 12 months due to non-cardiological origin.
- 7. Participation in another clinical trial with intervention.

5.3. Variables

- 1. Primary efficacy variable: combined 30-day outcome of all-cause mortality, heart failure (HF) readmission, or HF-related visits requiring diuretic treatment adjustment.
- 2. Secondary efficacy variable: individual components of the main variable, proportional change in natriuretic peptides and CA125 between admission and the first post-discharge outpatient visit, New York Heart Association functional class at the first post-discharge outpatient visit, average length of stay, cost of hospitalization for HF, and unplanned visit.
- 3. Primary safety variable: combined outcome of symptomatic systolic hypotension (<90 mmHg), electrolyte imbalances (potassium below 3 or above 5.5 meq/L), and/or worsening of renal function compared to the baseline visit at the first post-discharge outpatient visit (at least 50% reduction in glomerular filtration rate).

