The sample size estimation is based on the two previous studies by the group with this technology (references 19 and 20, which observed a Hazard ratio of 0.20 and 0.10 for the primary efficacy event respectively for ReDS-guided treatment) and on the average rate of the primary efficacy event (15%) of the participating hospitals during 2023. For an 80% power, a 5% alpha error, and considering a 10% subject loss rate during follow-up, 507 patients per group (1014 in total) are needed to detect a 50% reduction in the primary efficacy event (conservative estimate).

To evaluate the efficacy of the randomization process, a descriptive analysis will be performed using the chi-square test, Student's t-test, or Wilcoxon rank-sum test, as appropriate. All comparisons will be conducted according to the intention-to-treat principle. The time to the primary endpoint will be evaluated using Kaplan-Meier estimates and Cox proportional hazards models. A hierarchical analysis of the primary event with the win ratio method will also be performed. The number of patients needed to treat to prevent an efficacy event (NNT), and a safety event (NNH) will be calculated. For secondary outcomes, differences in plasma biomarker levels will be evaluated with chi-square, Fisher's exact test, t-test, and Wilcoxon rank-sum test, as appropriate. A p-value <0.05 will be considered statistically significant. The Stata program (StataCorp, Texas, USA) will be used.

Two interim analyses of the results are planned when 30% (risky estimate) and 60% (average estimate) of the sample size is reached. In addition, a steering committee of the clinical trial will be created, comprising members of recognized prestige ([name] [name], [name] [name], [name], [name], [name], [name], [name]), independent of the research team, who will ensure strict compliance with the protocol and have access to real-time event rates to detect potential futility of the intervention.

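### The renal part of the primary safety variable is read at one visit about 14 days after discharge, while the summary and objectives say 30 days; first-visit NYHA class has no place for death

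*Protocol*

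**What the plan says.** - **Safety variable, section 5.3.** The composite joins symptomatic hypotension, potassium outside limits, and "worsening of renal function compared to the baseline visit at the first post-discharge outpatient visit", the last defined as a GFR reduction of at least 50%. The visit phrase is attached to the renal part.
- **Safety timing elsewhere.** Section 1 states: "The primary safety endpoint will be the rate of symptomatic hypotension, electrolyte imbalances, or worsening renal function at 30 days". Objective 2.3 in section 4 compares the strategy "compared to standard clinical practice at one-month post-discharge by evaluating renal function deterioration", together with hypotension and electrolytes.
- **Secondary efficacy, section 5.3.** This includes "New York Heart Association functional class at the first post-discharge outpatient visit" and "proportional change in natriuretic peptides and CA125 between admission and the first post-discharge outpatient visit".
- **Visits, section 5.5.** The first clinic visit is 14 ± 3 days after discharge (the Summary says about 10 days) and the final visit is 30 ± 5 days after discharge. NYHA class and full bloods, including renal function, are taken at discharge, at the first visit and at the final visit.
- **Analysis, section 5.6.** "All comparisons will be conducted according to the intention-to-treat principle". The sample size is set "considering a 10% subject loss rate during follow-up". A number needed to harm (NNH) will be reported.
- **Hypothesis 2.3, section 3.** The ReDS strategy will be as safe as standard management.

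**The concern.** The protocol gives two time points for its primary safety variable. The narrower one, in the section that defines the variables, uses one of three scheduled post-baseline blood samples for the renal criterion. A fall at discharge that has recovered by day 14, a fall appearing between the first and final visits, and a fall followed by death before the first visit all go uncounted on that wording. Because the expected result is similar safety, missed renal events push towards the expected conclusion and make the NNH look more favourable.

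NYHA class has a related gap. A patient who dies before the first visit has no class there. Death is a component of the primary endpoint that the strategy is meant to reduce, so the patients with a value are partly selected by outcome and, if the strategy works, unequally by arm.

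**Working it through.** **1. The definitions side by side.** The last column takes the 30-day endpoint as any qualifying event up to the final visit.

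| Qualifying GFR fall | Section 5.3 as written | Any event to 30 days |
|---|---|---|
| Discharge sample only, recovered by first visit | not counted | counted |
| First visit | counted | counted |
| Final visit only | not counted | counted |
| Discharge sample, then death before first visit | not counted | counted |
| No sample after baseline, then death | not counted | needs a rule |

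Sections 1 and 4 do not say whether the 30-day endpoint is cumulative or a status on that day. A status reading would also disagree with section 5.3, because it would use the final visit and not the first.

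**2. The plan's own figures.** The protocol gives no visit-attendance figure to reproduce. From section 5.6 I take 15% events in control, a 50% reduction (7.5%), 10% loss and 507 per arm. The 507 serves only as a denominator. It does not follow from these inputs by the usual two-sided formula at 80% power (278 per arm; 278 / 0.9 = 309), but nothing below depends on that.

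**3. Patients unscored because of death.** Assumptions: half of the 30-day events precede the visit, and 10% to 30% of events are deaths. With all loss before the visit, the share added by death is (1 − loss) × event rate × death share × 0.5.

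- Control: 0.9 × 0.15 × 0.10 × 0.5 = 0.7% to 0.9 × 0.15 × 0.30 × 0.5 = 2.0%, or about 3 to 10 of 507.
- ReDS: 0.9 × 0.075 × 0.10 × 0.5 = 0.3% to 0.9 × 0.075 × 0.30 × 0.5 = 1.0%, or about 2 to 5 of 507.
- With the 10% loss, the total is 10.3% to 12.0%. If only half the loss precedes the visit, it is 5.4% to 7.1%.

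The difference between arms due to death is about 2 to 5 patients.

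**4. Adding other events that prevent the visit.** If a share f of all primary events prevents attendance, then 507 × rate × f gives, control v ReDS: 8 v 4 (f = 10%), 19 v 10 (25%) and 38 v 19 (50%). The last is an upper illustration, because visits for diuretic adjustment are primary events but need not stop a patient attending.

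**5. Safety illustration (upper bound).** Assumptions, none from the protocol: true composite rates of 10% v 16%; 11% unscored per arm; being unscored is k times as likely after a safety event, k = 1 to 3. The whole composite is treated as bound to the visit. The unscored share among patients without an event is u = 0.11 / (1 + (k − 1)p).

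- k = 1, complete cases: 6.0 points, NNH 1 / 0.060 = 16.7. With unscored taken as no event: 0.89 × 6.0 = 5.3 points, NNH 18.7.
- k = 3: u = 0.11 / 1.20 = 0.0917 and 0.11 / 1.32 = 0.0833, so scored events are 0.10 × (1 − 0.275) = 7.25% and 0.16 × (1 − 0.25) = 12.0%. With unscored taken as no event: 4.75 points, NNH 21.1. Complete cases: 4.75 / 0.89 = 5.3 points, NNH 18.7.

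The standard error at 507 per arm is √[(0.09 + 0.1344) / 507] = 2.1 points, so the complete-case shift of at most 0.7 points is about one third of it. Power falls from 81% to 73–77%. The step from 81% to 77% is only the loss of 11% of patients.

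**6. Biomarkers.** Bias ≈ (difference between arms in unscored share) × (gap between unscored and scored patients). From step 4 with 10% loss, the difference is 0.9 × (0.15 − 0.075) × f = 0.7 to 3.4 points for f = 10% to 50%. With an assumed gap of 1 SD, the bias is 0.01 to 0.03 SD, against a standard error of √(2 / 456) = 0.07 SD, where 456 = 507 × 0.9.

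**The case against.** The strongest reply is that rules for death and missing values usually belong in a statistical analysis plan, which is not shown here. That stands for ordinary missing data and for the biomarkers. It does not remove the conflict on the safety time point, which lies within the protocol. Nor does it change the fact that section 5.3 itself fixes which GFR value counts.

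A reader might infer more, and the documents do not support it:

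- **That intention-to-treat is broken.** The principle concerns analysis by assigned arm. Incomplete secondary data strain it but do not contradict it.
- **That these patients cannot be scored.** The protocol nowhere says they are excluded or counted as event-free. The rank-sum test in section 5.6 can take death as the worst rank. A readmitted patient may attend later.
- **That the whole safety composite is lost with the visit.** Hypotension and potassium are not clearly tied to it, so a patient who dies in renal failure may still qualify through them. A blinded committee also reviews reported safety events (sections 5.9 and 7.5), although it cannot make a renal fall count that the definition leaves out.

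It is also fair to say that counting any event from randomisation alters the variable written in section 5.3, and that death as an event brings an efficacy component into safety. For that reason the death version belongs in a sensitivity analysis.

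**Conclusion.** The point holds as a badly fixed endpoint definition. The renal part of the primary safety variable has two incompatible time points, and the one in section 5.3 ignores two of the three scheduled post-baseline samples and any fall followed by death before the first visit. First-visit NYHA class gives no place to death.

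The size is modest. Deaths add about 0.3 to 2.0 percentage points of unscored patients to the planned 10% loss, if half the events precede the visit and 10% to 30% of events are deaths. The safety illustration moves a 6.0-point excess to between 4.75 and 6.0 points, on assumed rates and as an upper illustration. Biomarker bias is negligible. The number of renal falls missed because they show only at discharge or at the final visit cannot be estimated from the protocol. The time-to-event primary endpoint is not affected. The change is worth making because the direction of error favours the expected safety conclusion and the data to avoid it are already scheduled.

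**What to change.** 1. Reconcile section 5.3 with the Summary and Objective 2.3, so that the safety variable has one time point. State that the 30 days run from discharge, as in Objective 2.3 and the visit schedule.
2. Count the safety composite as any qualifying event from randomisation to 30 days, using every scheduled sample: discharge, first visit and final visit.
3. Report beside the NNH a sensitivity version in which death before assessment counts as an event.
4. Analyse first-visit NYHA class as an ordinal outcome with death as the worst category, by the rank-sum test already named.
5. Optional: a mixed model for log natriuretic peptide and log CA125 using the scheduled post-baseline samples.

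The cost is protocol wording and a little more analysis. The safety count will be somewhat higher and less specific to one visit, and a death-ranked NYHA result is slightly harder to read than one among survivors.

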5.4. Protocol

Patients will be identified and selected upon admission. If they meet the selection criteria and confirm their willingness to participate in the study, they will be randomized in a 1:1 sequence through a mobile application specifically designed for the study by P INVESTIGA, to one of the following interventions within 48 hours of hospital arrival:

1) "ReDS-guided strategy." Each day, the clinician responsible for the patient will have access to the ReDS value and will adjust the treatment according to the study's diuretic protocol (annex 3). The responsible physician can discharge the patient if the clinical stability criteria are met, and the ReDS value is below 35% and/or a reduction of 15% or more from the admission ReDS value has been achieved. If the ReDS criteria are not met, the patient must remain hospitalized for another day until these conditions are met. Clinical stability is defined as the presence of at least 2 of the following 3 conditions: i) discharge weight lower than admission weight, ii) at least a 20% reduction in natriuretic peptide from admission, and iii) a score <2 in the Orthoedema score.

2) "Usual clinical practice strategy." The responsible physician will not have access to the ReDS values and will adjust the treatment according to their clinical judgment and local practices. Discharge can be given if the clinical stability criteria are met.

The ReDS technology has been described in detail previously (7, 8, 20). Briefly, the ReDS system consists of 2 sensors that are placed (sitting or supine) on the front (infraclavicular) and back (below the scapula) of the patient's right hemithorax and in 45 seconds accurately quantifies the proportion of fluid in the lung. The sensors are connected via 1 cable to a touchscreen monitor that easily guides the measurement process and stores this information. The accuracy of this technology has been validated with high-resolution chest computed tomography (8) and invasive hemodynamic measurements with a Swan-Ganz catheter (9). Normal ReDS values range between 20% and 35% (i.e., 20-35% of the lung would be fluid). Above 35% is considered congestive, whereas below 20% the lung would be "dry" or dehydrated.

A ReDS device will be distributed per center with a unique serial number, ensuring traceability. Prior training will be provided to the research and clinical staff (both medical and nursing) of each participating center before the study begins by the company distributing the device in Spain (SOREVAN). The prior training for using this technology is very simple, with a learning curve of less than 1 hour, although each participating center already has previous experience with this technology. The device itself guides the operator through a touchscreen before a measurement, graphically informing each step to take to perform a measurement on a patient. The ReDS devices used in the clinical investigation will be utilized following their instructions for use.

5.5. Data collection and management

All information at admission, during hospitalization, at discharge, and during the 2 post-discharge outpatient visits will be collected by the researchers in an electronic data collection notebook (CRD) through a mobile application that allows semi-automatic and

anonymized extraction of relevant clinical information by photographing medical reports. The mobile phone application will be developed by P INVESTIGA, a company with extensive experience in this type of app. Specifically, the following will be collected:

5.5.1 Baseline visit (within first 48 hours of hospital admission)

- Informed consent with date and signature of the patient and local investigator.
- Demographic data: race, gender, and age, and anthropometric data: weight and height.
- Complete medical history, including main comorbidities and usual medical treatment.
- Usual NYHA functional class before decompensation.
- Vital signs (blood pressure, heart rate, arterial saturation) and daily physical examination findings (weight, signs of left and right congestion).
- 12-lead ECG.
- Baseline echocardiogram (or the last available in the year before the current admission).
- Complete blood tests (renal and liver function, electrolytes, lipid profile, NTproBNP/BNP, CA125, blood count, and coagulation).
- Alternative methods for congestion analysis used by local clinical practice: lung ultrasound, VExUS, impedance, right heart catheterization.
- Measurement with the ReDS system.

5.5.2. Follow-up visits (every day during admission):

- Vital signs (blood pressure, heart rate, arterial saturation) and daily physical examination findings (weight, signs of left and right congestion).
- Measurement with the ReDS system
- Alternative methods for congestion analysis used by local clinical practice: lung ultrasound, VExUS, impedance, right heart catheterization.

5.5.3. Visit at discharge (within 24 hours before hospital discharge):

- Current NYHA functional class at discharge.
- Vital signs (blood pressure, heart rate, arterial saturation) and daily physical examination findings (weight, signs of left and right congestion).
- 12-lead ECG.
- Echocardiogram at discharge (not mandatory).
- Complete blood tests (renal and liver function, electrolytes, lipid profile, NTproBNP/BNP, CA125, blood count, and coagulation).
- Alternative methods for congestion analysis used by local clinical practice: lung ultrasound, VExUS, impedance, right heart catheterization.
- Measurement with the ReDS system
- Major interventions performed during the index admission: revascularization, electrical cardioversion, arrhythmia substrate ablation, device implantation, complications, etc.

5.5.4. First visit at HF Clinic (14 +/- 3 days after hospital discharge):

- Current NYHA functional class.
- Vital signs (blood pressure, heart rate, arterial saturation) and daily physical examination findings (weight, signs of left and right congestion).
- 12-lead ECG.

- Complete blood tests (renal and liver function, electrolytes, lipid profile, NTproBNP/BNP, CA125, blood count, and coagulation).
- Alternative methods for congestion analysis used by local clinical practice: lung ultrasound, VExUS, impedance, right heart catheterization.
- Measurement with the ReDS system.
- Clinical events.

5.5.5. Final visit at HF Clinic (30 días+/-5 days after hospital discharge):

- Current NYHA functional class.
- Vital signs (blood pressure, heart rate, arterial saturation) and daily physical examination findings (weight, signs of left and right congestion).
- 12-lead ECG.
- Complete blood tests (renal and liver function, electrolytes, lipid profile, NTproBNP/BNP, CA125, blood count, and coagulation).
- Alternative methods for congestion analysis used by local clinical practice: lung ultrasound, VExUS, impedance, right heart catheterization.
- Measurement with the ReDS system.
- Clinical events.

The information will be stored in a restricted-access online database developed by P INVESTIGA. Only designated researchers at each center will have access to this information.

After entering the data into the system, it will be automatically reviewed with monthly scheduled quality checks. Errors, discrepancies, missing data, and out-of-range entries will be resolved both automatically and manually (by the clinical monitor and data manager) generating data queries. The system will provide detailed query process control. Corrections to the electronic CRD can only be made by specially designated personnel and must be signed by the researcher. All changes will be automatically recorded in the system's audit trail. An authenticated user account will be created and maintained by P INVESTIGA for each authorized user once they have completed the corresponding training. Users must keep their passwords confidential. Depending on their role within the clinical study, users may be limited to viewing the information only or have additional permissions to enter and correct data, generate query resolutions, and provide electronic signatures. Only researchers will be able to sign clinical entries. All electronic documents related to the study will be stored in the archive generated by P INVESTIGA, allowing storage under conditions protected from fire, flood, theft, or pests. Access to the archives will be controlled. After the database is closed, all data from the electronic CRF, as well as the change control performed, will be exported and electronically stored in the server archive. The research team will keep this information stored for at least 15 years after the completion of the study and will be obligated to make the information accessible upon request by the Ethics Committee, regulatory agencies, or monitoring and auditing company. At the end of this period, local laws and regulations will be considered to decide whether to extend the retention period or proceed with the destruction of the data.

Data safety

The study will be carried out while always maintaining confidentiality in accordance with current legislation (Regulation (EU) 2016/679 of the European Parliament and of the Council of 27 April 2016 on Data Protection (GDPR), Organic Law 3/2018 of 5 December on the Protection of Personal Data and guarantee of digital rights, and the provisions in this regard contained in Law 41/2002 of 14 November, the basic law regulating patient autonomy and rights and obligations in the matter of information and clinical documentation, as well as any applicable and relevant regulations).

5.6. Sample size estimation and data analysis

The sample size estimation is based on the two previous studies by the group with this technology (references 19 and 20, which observed a Hazard ratio of 0.20 and 0.10 for the primary efficacy event respectively for ReDS-guided treatment) and on the average rate of the primary efficacy event (15%) of the participating hospitals during 2023. For an 80% power, a 5% alpha error, and considering a 10% subject loss rate during follow-up, 507 patients per group (1014 in total) are needed to detect a 50% reduction in the primary efficacy event (conservative estimate).

To evaluate the efficacy of the randomization process, a descriptive analysis will be performed using the chi-square test, Student's t-test, or Wilcoxon rank-sum test, as appropriate. All comparisons will be conducted according to the intention-to-treat principle. The time to the primary endpoint will be evaluated using Kaplan-Meier estimates and Cox proportional hazards models. A hierarchical analysis of the primary event with the win ratio method will also be performed. The number of patients needed to treat to prevent an efficacy event (NNT), and a safety event (NNH) will be calculated. For secondary outcomes, differences in plasma biomarker levels will be evaluated with chi-square, Fisher's exact test, t-test, and Wilcoxon rank-sum test, as appropriate. A p-value <0.05 will be considered statistically significant. The Stata program (StataCorp, Texas, USA) will be used.

Two interim analyses of the results are planned when 30% (risky estimate) and 60% (average estimate) of the sample size is reached. In addition, a steering committee of the clinical trial will be created, comprising members of recognized prestige ([name] [name], [name] [name], [name], [name], [name], [name], [name]), independent of the research team, who will ensure strict compliance with the protocol and have access to real-time event rates to detect potential futility of the intervention.

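### Short-lived safety events between the baseline and discharge samples are neither systematically collected nor clearly counted, and the safety window is stated in three different ways

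*Protocol*

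**What the plan says.** **Safety variable.** Protocol 5.3 combines symptomatic hypotension with "electrolyte imbalances (potassium below 3 or above 5.5 meq/L), and/or worsening of renal function compared to the baseline visit". The renal criterion is a fall in filtration rate of at least 50%, and the sentence ties it to the first outpatient visit after discharge.

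**Treatment phase.** In the ReDS arm (5.4), "Each day, the clinician responsible for the patient will have access to the ReDS value and will adjust the treatment according to the" diuretic table in Annex 3.

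**Data collected.** The visit lists in 5.5.1 to 5.5.5 give:

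- Daily, under "Follow-up visits (every day during admission", the Protocol lists three items, of which the first reads "Vital signs (blood pressure, heart rate, arterial saturation) and daily physical examination findings (weight, signs of left and right congestion"; the others are the ReDS measurement and any local congestion methods. Nothing else is listed.
- At baseline, discharge and both outpatient visits: "Complete blood tests (renal and liver function, electrolytes, lipid profile, NTproBNP/BNP, CA125, blood count, and coagulation". The discharge list is headed "Visit at discharge (within 24 hours before hospital discharge".
- At discharge: "Major interventions performed during the index admission: revascularization, electrical cardioversion, arrhythmia substrate ablation, device implantation, complications, etc".
- At the two outpatient visits only: a clinical-events item.

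**Event reporting.** Section 5.12.6 tells the investigator to document all events in the CRFs, with serious events due within 24 h of detection. Sections 5.9 and 7.5 provide for committee review of events, blinded to group according to 5.9.

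**The concern.** Two of the three safety components are laboratory thresholds. The schedule has no laboratory value on the hospital days between baseline and discharge, when Annex 3 decisions are made daily in one arm. A potassium or filtration-rate excursion that appears and is corrected within that interval reaches the data only if local care samples it and someone reports it as an event.

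Hypothesis 2.3 expects the strategy to be no less safe than usual management. For a claim of that kind, missed events tend to make the arms look alike, so incomplete capture favours the hoped-for conclusion. Section 5.8 also plans to look at safety variables at 30% and 60% of the sample, so the same gap would carry into those reviews.

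**Working it through.** The plan gives no figure to reproduce here. The check sets the safety variable against the visit lists, then compares the stated windows.

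**Step 1: scheduled sources for each component (5.3 against 5.5.1 to 5.5.5).**

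| Component | Baseline | Hospital days between | Discharge | Two outpatient visits |
|---|---|---|---|---|
| Potassium | yes | no | yes | yes |
| Renal function | yes | no | yes | yes |
| Blood pressure | yes | yes, daily | yes | yes |
| Clinical-events item | no | no | no (complications only, inside the interventions item) | yes |

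Potassium and renal function therefore have 4 scheduled time points: 2 in hospital, 2 after discharge, and 0 on the days between baseline and discharge. The clinical-events item has 2, both after discharge. Hypotension counts only when symptomatic. The pressure is seen daily, but no daily field is listed for the symptom.

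**Step 2: length of the unsampled interval.** The Protocol gives no length of stay, so a stay of L = 5 to 10 days is an assumption.

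- Baseline sample on day 1, discharge sample on day L: days without a scheduled sample = L − 2, which is 5 − 2 = 3 to 10 − 2 = 8.
- Baseline sample on day 2 (5.5.1 allows 48 h): L − 3, which is 2 to 7.

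These are unsampled days, not missed events. The interval can also differ by arm: in 5.4 a ReDS-arm patient who misses the ReDS criterion stays another day, and usual care has no matching rule.

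**Step 3: does general event reporting fill the gap?** Section 5.12 defines device-related and serious events. Nothing in it says that a potassium or filtration-rate value beyond the 5.3 limits must be reported. Adjudication under 5.9 covers reported events, so it cannot recover what was never recorded.

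**Step 4: the window.**

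- Summary: at 30 days, with no starting point.
- Section 4, objective 2.3: one month after discharge.
- Section 5.3: the first outpatient visit after discharge (14 ± 3 days in 5.5.4), at least for the renal component.

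These are three different windows. None says whether an event between randomisation and discharge counts. If such events count, data collection does not fully support them. If they do not, the primary safety variable leaves out the phase of daily Annex 3 decisions.

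**The case against.** The strongest reply is that inpatient harm is far from unobserved. Blood pressure is taken every day. A renal or potassium disturbance still present at the end of inpatient treatment is caught by the discharge sample in both arms. Complications are noted at discharge, all events must be documented, and reported ones go to a blinded committee. Section 5.9 also separates the researchers from the treating team. All of this stands. A reader might infer from the visit lists that the safety endpoint is blind in hospital; the documents do not support that. What remains open is the short-lived laboratory change and the symptom of hypotension.

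A reader might also infer that Annex 3 changes treatment every day. It does not: it calls for a daily decision, and its 20-35% row keeps the prescribed dose.

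A further reply is that the renal component, as written in 5.3, compares an outpatient value with baseline and needs no daily laboratory values. That is correct for that wording. It does not settle the other components, nor the conflict with section 4 and the summary.

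Finally, counting any qualifying value among routinely drawn samples could make matters worse. An any-time threshold gains events as sampling increases, and treating clinicians see ReDS values in one arm only. This is a sound objection, so such values should not enter the primary composite.

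**Conclusion.** The point holds at moderate severity. Short-lived safety events between the baseline and discharge samples are not systematically captured, and the Protocol does not say whether inpatient events count. Both weaken a conclusion of equal safety. Primary efficacy is not affected, and harm that persists to discharge or is reported is captured.

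The effect on the safety comparison cannot be computed, because the Protocol gives no safety event rate. The 3 to 8 unsampled days (2 to 7 with a day-2 baseline) rest on the assumed stay of 5 to 10 days. A reader might infer that the safety result will be biased by a known amount or in a known direction. The documents show only that under-ascertainment would tend to make the arms look alike and that sampling frequency may differ between them; they do not show that it does. That in-hospital values are not collected is read from the visit lists, since the CRF itself is not shown.

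**What to change.** 1. In 5.3, section 4 and the summary, state one safety window that starts at randomisation and includes the index admission. Give one end point, and say whether its days are counted from randomisation or from discharge.
2. Add a clinical-events item, naming symptomatic hypotension, to 5.5.2 and 5.5.3 in both arms.
3. For the primary safety composite, evaluate the potassium and filtration-rate components at the samples already scheduled in both arms, including the discharge sample.
4. Record routinely drawn in-hospital potassium and creatinine values with their dates in both arms. Use them only in a supportive any-time analysis, reported with the number of samples per arm.

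Item 3 still leaves a laboratory change that resolves before discharge outside the primary composite. Item 4 makes it visible without letting unequal sampling drive the main comparison.

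**Cost.** A few extra CRF fields, which the study application can help fill because 5.5 already provides for "anonymized extraction of relevant clinical information by photographing medical reports". No extra blood draws are needed. The safety event rate will be somewhat higher. Under 5.13 a change to study procedures or data analysis is a substantial amendment, so ethics committee approval is needed before it takes effect.
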